1 BACKGROUND

Neonatal Abstinence Syndrome (NAS) refers to a variety of withdrawal symptoms, particularly prevalent in newborns with opioid exposure. Clinically significant neurobehavioral symptoms include pathophysiological cardio-respiratory instabilities, gastrointestinal dysfunction, hypersensitivity, and sleep disruption. There is a critical need to develop non-pharmacological interventions for managing withdrawal in newborns to reduce withdrawal symptoms, facilitate weaning, decrease pharmacotherapy, and provide additional intervention for infants in whom pharmacological treatment is insufficient. Growing research suggests the importance of sensory tactile stimulation for promoting physiological maturation, brain development, and stability of function, and for improving behaviors implicated in intrauterine drug exposure. Evidence supports that low-level, stochastic (random) stimulation can promote stability in destabilized biological systems, including improved transduction of cutaneous mechanoreceptors in animals, sensory perception in adults, and improved cardio-respiratory function in premature infants. Our recent pilot data suggests that acute presentation of low-level stochastic vibratory stimulation (SVS) delivered through a uniquely-constructed crib mattress improves physiological function in drugwithdrawing infants. We hypothesize that stochastic resonance may affect somatosensory and vestibular systems by facilitating more accurate detection of sensory inputs (e.g., touch, auditory) and increase neural stability. For example, SVS may stimulate pressure receptors to improve vagal tone and cardiac activity, and impinge upon respiratory oscillators to enhance respiratory function. The main objective of this proposal is to test whether early intervention (initiated within 24 hours post birth) and daily administration of SVS reduces withdrawal and improves neurobehavioral outcomes.

1.1 Trial Objectives

This study investigates Stochastic Vibrotactile Stimulation (SVS) complementary to standard of care for treating NAS. Using a specially-constructed crib mattress we will determine if SVS reduces symptoms and duration of NAS and improves long term outcomes in intrauterine opioid-exposed newborns. Findings from this study will elucidate whether SVS has potential as a therapeutic treatment for drug-exposed newborns to reduce symptomatology, facilitate weaning and minimize hospitalization, with implications for better regulation of systems and improved developmental outcomes.

1.1.1. Specific Aims. The three areas to be investigated in this project are:

Specific Aim 1. Determine the efficacy of SVS as a non-pharmacological therapy complementary to standard clinical care (SCC) for reducing severity and duration of opioid withdrawal in newborns compared to SCC alone. Quantify clinical variables: NAS severity/administration of treatment, treatment days, days in hospital, velocity of weight gain, cumulative morphine dose, and longitudinal assessment of movement activity.

Specific Aim 2. Examine physiological responses to SVS compared to SCC at two stages of withdrawal severity. Measure cardio-respiratory stability, temperature regulation, and movement activity.

Specific Aim 3. Compare neurobehavioral outcomes in fetal drug-exposed infants between infants who received SVS and those who received SCC. Examine longitudinal outcomes assessments at 1 month, 6-months and 1 year to test whether early intervention with SVS compared to SCC improves physical, social, emotional and cognitive development.

2 SUMMARY OF THE PROTOCOL

2.1 Brief Description of the Protocol (Study Design)

The proposed experiments aim to examine whether SVS, using a specially-designed crib mattress, has potential as a complementary treatment of NAS. We will determine if SVS reduces NAS severity (administration of treatment/treatment days), cumulative morphine dose and days in hospital, reduces specific physiological markers of withdrawal (excessive movement and cardio-respiratory instabilities), and improves neurodevelopment outcomes in the first year of life.

NOTE: All changes to the protocol must be approved by NIDA prior to implementation.

2.1.1. Investigational Device. Stochastic Vibrotactile Stimulation (SVS). The

infant's crib mattress will be replaced with a specially constructed mattress (noncommercially available) to provide gentle vibrations and sounds during mattress stimulations. The mattress is embedded with mechanical actuators that provide wholebody SVS (30-60Hz; ~10-12µm RMS). Co Fab Design, LLC will construct the mattresses and drivers as per the design documents furnished under Confidentiality Disclosure Agreement (CDA; University of Massachusetts Medical School/Wyss Institute-Harvard University patent: PCT/US2015/021999) for research purposes only as per the licensed mattress assembly and electrical assembly and verification documentation; device components may be modified with improved technologies that provide equivalent mattress output to help ensure consistency of mattress integrity over time. Engineers from the Wyss Institute and the University of Pittsburgh will provide assistance in the build to ensure it performs as per the original patent documentation.

2.1.2. Study Design/Type. This study is a randomized, placebo-controlled, parallel group clinical trial. Eligible patients will be randomized into one of two groups in a 1:1 ratio, matched for gender, to either (1) SVS or (2) SCC:

1) SVS. Experimental Intervention: Newborn infants at-risk for NAS due to opioid exposure *in utero* randomized to this arm will receive daily intervals of continuous SVS (ON) and no SVS (OFF) throughout hospitalization, starting within 30-hrs post birth. An automated control box will be set to deliver continuous alternating 3-hr cycles of ON/OFF intervals. A stimulation period will always be followed by an interval of no stimulation; in any 24-hr period an infant will not receive more than a total of 12 hrs of stimulation (should the infant remain in the crib throughout an entire 24 hr period). Notably, infants are not always in their crib and it is not feasible to provide round-the-clock research staffing to monitor when the infant is in or out of the crib (e.g., being held

by caregiver, fed, in motorized bedside glider – all part of the standard of care). The preprogrammed 3-hr duty cycle, 24/7, affords opportunity to capture periods when the infant is in the crib, and also conforms to routine timing of medication. Periods of stimulation will be complementary to standard of clinical care (e.g., clinically-determined pharmacological management; routine holding by caregiver or hospital-issued motorized glider; breast and/or bottle feed). A bedside log will indicate periods the infant is in the crib, being held, or placed in hospital-issued gliders/motorized seats. Infants will be scored for severity of withdrawal using standardized, modified Finnegan scoring system by clinical-care nurses per routine clinical care throughout hospitalization, and may receive pharmacological treatment as per standard care determined by the medical-care team at the respective institution.

2) SCC. No Intervention: Standard of Clinical Care (SCC). Newborn infants atrisk for NAS due to opioid exposure in utero randomized to this arm will be enrolled within 30-hours post birth and receive standard of care (e.g., clinically-determined pharmacological management; routine holding by caregiver or hospital-issued motorized glider; breast and/or bottle feed). Infants will be issued a hospital crib mattress. A bedside log will indicate periods the infant is in the crib, being held, or placed in hospital-issued gliders/motorized seats. Infants will be scored for severity of withdrawal using standardized, modified Finnegan scoring system by clinical care nurses per routine clinical care throughout hospitalization, and may receive pharmacological treatment as per standard care determined by the medical-care team at the respective institution.

2.1.3. Study Site. Studies will be conducted at the UMass Memorial Healthcare Neonatal Intensive Care Unit (NICU), Continuing Care Nursery (CCN), and Newborn Nursery (NN) – referred to as UMass - and at the Magee-Women's NICU and Well-Baby Nursery, and Mercy Hospital, of the University of Pittsburgh Medical Center – referred to as UPitt - where infants receive round-the-clock medical care. Studies for Aim 1 and Aim 2 will be performed at the infant's hospital bedside, outcome assessments for Aim 3 will be performed at respective hospital inpatient (if infant still hospitalized) and outpatient facilities.

2.1.4. Study Duration. Subjects will participate in the study throughout their hospitalization, beginning within 30 hours post birth, and will be followed for up to 14 months post post-hospital discharge via medical records, telephone interviews, and return visits for outcome assessments.

2.1.5. Randomization. Random allocation of subject to treatment (SVS or SCC) will involve a permuted block design with random block sizes to assure equal treatment assignment for both treatments. We will stratify the randomization process by clinical site to force a balance between treatment groups and gender within each site. The random treatment assignments will be generated in SAS and uploaded into the IVRS system. The randomization process will verify patient eligibility before issuing treatment assignment. Treatment assignments will be in the form of mattress assignment tracked by the IVRS system based on admission and discharge information entered into REDCap (**See 4.2 below**). The IVRS system can be accessed by certified study staff

either through a telephone call or over the internet to a secure web site. The treatment assignments are recorded automatically in the REDCap system through an interface between the two systems and cannot be modified once imported from the IVRS system. The randomizations are monitored and verified by study staff on a routine basis. The IVRS also will monitor mattress availability and will notify study staff if a mattress of each type is not available for a randomization. (Maternal exposure will be stratified in the analysis).

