2.3 Inclusion/Exclusion Criteria

A total of 230 full-term (>37wks gestational age) newborn infants exposed to opioids *in utero* will be studied over the five-year funding period: 100 at UMass and 130 at UPitt.

2.3.1. Inclusion Criteria. Infant inclusion criteria include documented opioid drug exposure (i.e., positive toxicology screen; exposure questionnaire and medical record history) and comprise the general population (Worcester, MA and Pittsburgh, PA demographics) without restriction in regard to gender, race or socioeconomic status. Infants may also have additional prenatal poly-drug exposure (e.g., benzodiazepines, barbiturates, amphetamines, cannabinoids, alcohol, nicotine and/or caffeine). Inclusion of pregnant women is for the sole purpose of obtaining consent to study the infant post-delivery, and to review infant and maternal medical records. Pregnant women are included because we will be recruiting pregnant women who are at risk for delivering infants with NAS due to drug exposure in utero. Prenatal consents are needed to help expedite feasibility of study of infants soon after delivery. Infants will not be studied in utero, but will only be studied after delivery.

2.3.2. Exclusion Criteria. Subjects with clinically significant fetal anomaly, congenital abnormality, adverse pregnancy outcome, hydrocephalus or intraventricular hemorrhage >grade 2, seizure disorder not related to drug withdrawal, clinically significant cardiac shunt, anemia (hemoglobin<8g/dL), requires mechanical respiratory support or is being treated for MRSA or infection at the time of the study will be excluded, or other medical condition aside from NAS will be excluded. Informed consent will be obtained from parent(s) or legal guardian of all participants.

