4.3. Data Analysis Plan

4.3.1. Overview. Table 1 provides a summary list of outcome variables for each Specific Aim. Descriptive statistics will be calculated (means/SD or median/IQR) by treatment group. Because infants will be repeatedly observed and measured, initial analyses comparing outcomes between the treatment groups (SVS vs SCC) will be conducted using standard approaches assuming a normal distribution (i.e., two-sample t-test) or using non-parametric alternatives if assumption of a normal distribution is not appropriate (i.e., Mann-Whitney U Test). We will use mixed effect models to analyze the repeated measures over time. These models will estimate the trajectory of outcomes over time within each treatment group as affected by condition and other factors of interest. The time metric for these models will be hrs since birth for Aims 1 and 2 for each measurement so that the trajectories will relate to the same baseline

measurement for all infants. Treatment group will be considered as fixed effect in the models, with other factors considered to be either fixed or random effects, depending on the nature of the factor: opioid only vs opioid+other; gender, delivery mode (vaginal or caesarean-section); delivery anesthetics (none vs anesthetics). Comprehensive histories from medical record and questionnaire will allow us to examine the influence of additional variables

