4.3.2 Specific Aim 1: We will use mixed effects models as described above to examine whether infants treated with SVS compared to SCC have: 1) Lower daily average and maximum NAS scores; 2) Less morphine requirement (primary pharmacological treatment for managing NAS at both sites; cumulative dose normalized for body weight); 3) Enhanced velocity of weight gain throughout hospitalization; and 4) Shorter hospitalization length of stay. A model will be fit for each outcome using Nagelkerke's R² to determine the model with the best fit using the ratio of the -2 log likelihoods for the model with covariates compared to the intercept-only model. Factors of interest will be included in the model as appropriate and interactions with treatment group will be tested as well. The interactions will indicate whether the treatment effect is the same across subgroups. Additional analyses to identify groups of infants who do particularly well (or poorly) with SVS will be conducted using latent class techniques, such as cluster analysis (for continuous variables) or latent class analysis (for discrete variables). The factors of interest will include: drug exposure (e.g., prescribed maintenance therapy, prescription drugs and illicit substance; with or without poly-drug use), demographic data (gender, race, gestational age, birth weight, birth head circumference, delivery mode, anesthesia at delivery), and feed type (formula or breast milk).

Movement: Actigraphy (movement activity frequency) will be compared across days and between Groups using similar mixed effects models as above. The outcomes of interest are actigraphy throughout hospitalization to determine if SVS reduces movement and increases quiescence episodes over time (12 and 24 hour assessments) compared to SCC.

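### Only site is named as a randomisation stratum although gender balance is promised, and site is missing from the Aim 1 and Aim 3 models

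*Combined protocol and SAP*

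**What the plan says.** **Allocation.** Section 2.1.5 describes a "permuted block design with random block sizes to assure equal treatment assignment for both treatments" and continues: "We will stratify the randomization process by clinical site to force a balance between treatment groups and gender within each site". Section 2.1.2 says: "Eligible patients will be randomized into one of two groups in a 1:1 ratio, matched for gender". No section lists gender as a stratum, gives a matching procedure or names a minimisation factor. For one other factor, 2.1.5 does say where it is handled: "Maternal exposure will be stratified in the analysis". Block sizes are not given. Section 2.3 gives the numbers: infants "will be studied over the five-year funding period: 100 at UMass and 130 at UPitt".

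**Analysis.** Besides treatment, 4.3.1 names these model factors: "opioid only vs opioid+other; gender, delivery mode (vaginal or caesarean-section); delivery anesthetics (none vs anesthetics". Section 4.3.2 (Aim 1) adds drug exposure, "demographic data (gender, race, gestational age, birth weight, birth head circumference, delivery mode, anesthesia at delivery), and feed type (formula or breast milk". Factors enter at the analyst's discretion, with model fit judged by Nagelkerke's R². Section 4.3.4 (Aim 3) reuses that strategy. Gender is in both lists and site is in neither.

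**Sites.** Treatment is decided by each institution's own care team (2.1.2), and Finnegan scoring is done by nurses trained at each site (4.1.1). Table 4 shows different regional maternal populations: African American 5.3% at UMass and 19.7% at UPitt, Hispanic or Latino 10.5% and 1.1%. Aim 2 is done at UMass only (Table 1 and 4.1.2).

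**The concern.** There are two gaps.

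First, the mechanism named does not produce the property claimed. Blocks within site keep the arms equal in size at each site and leave the gender split between arms to chance. A programmer working from 2.1.5 could reasonably build a list with two strata, and the promised balance would then not be forced.

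Second, the one factor that is certainly a stratum appears in no analysis model. If the sites score, treat or discharge differently, the between-site difference stays in the residual variance. The model then reports a standard error larger than the design delivers, and precision is lost. Length of stay and cumulative morphine, both Aim 1 outcomes, depend most directly on local practice. The initial two-sample tests in 4.3.1 adjust for neither site nor gender, and the later models adjust for gender only if it is selected.

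**Working it through.** **1. The plan's own figure.** Section 2.4.1 gives 115 per group, SD 2.5, two-sided alpha 0.05 and a detectable difference of 1.1 at 90% power.
- Standard error = 2.5 × √(2/115) = 0.330.
- Detectable difference = 0.330 × (1.960 + 1.282) = 1.07, which rounds to 1.1.
- Power at exactly 1.1 = Φ(1.1/0.330 − 1.960) = 0.916 (0.913 with the exact t-test). The figure reproduces.

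**2. Gender balance if site is the only stratum.** Assume 50% male (not in the documents) and equal arms within site. The difference in male share between arms has SD √(0.25 × 2/n), with n per arm.

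| | n per arm | SD (points) | 10 points in SDs | Two-sided tail |
|---|---|---|---|---|
| Overall | 115 | 6.6 | 1.52 | 13% |
| UMass | 50 | 10.0 | 1.00 | 32% |
| UPitt | 65 | 8.8 | 1.14 | 25% |

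At UMass a gap of 10 points is exactly 5 infants, so the result depends on whether exactly 10 is counted. The count difference has SD √(100 × 0.25) = 5. With a continuity correction, the chance of 5 or more is the tail beyond 4.5/5 = 0.9, or 37%. The chance of 6 or more is the tail beyond 5.5/5 = 1.1, or 27%. The 32% lies between.

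A simulation of permuted blocks with assumed block sizes 2/4, 4/6 or 4/6/8 gave these chances of a gap of 10 points or more: about 13% overall, 35–37% at UMass and 26–27% at UPitt. The 95th percentile of the gap was about 13 points overall, 20 at UMass and 17 at UPitt.

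**3. The same with site-by-gender strata.** The overall 95th percentile fell to 1.7–1.8 points, and no simulated trial reached 10.

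**4. Site left out of the Aim 1 model.** Take the single-time-point comparison of 2.4.1. Assume a within-site SD of 2.5, arms balanced within site, and a site difference D, for which the documents give no value. The site shares are 100/230 and 130/230, with product 0.2457.
- SD seen by the model without site: √(2.5² + 0.2457 D²).
- Actual standard error of the treatment difference: 0.330, because allocation is balanced within site.
- Let r be the ratio of the first SD to 2.5. Type I error = 2[1 − Φ(1.960 r)]. Power = Φ(1.1/0.330 − 1.960 r).

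| D (points) | r | Type I error | Power without site | Power with site |
|---|---|---|---|---|
| 0 | 1.000 | 0.050 | 0.916 | 0.916 |
| 1 | 1.019 | 0.046 | 0.910 | 0.916 |
| 2 | 1.076 | 0.035 | 0.890 | 0.916 |
| 2.5 | 1.116 | 0.029 | 0.875 | 0.916 |

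If the SD of 2.5 already contains between-site variation, power without site does not fall below 0.916 and adjustment raises it further. The repeated-measures figures in 2.4.1 were not recomputed.

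**The case against.** The best defence is that 2.1.5 and 2.1.2, read together, are a loose description of blocks within site by gender. A reader might infer that randomisation is stratified by site alone and that the promised balance will therefore not be delivered. The documents do not support that. They never say that site is the only stratum, and the wording of 2.1.2 points the other way. What can be said is that the role of gender in allocation is unspecified. The probabilities in step 2 of the working apply only under the site-only reading, and the 10-point threshold is a convenient benchmark not tied to any outcome effect.

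The consequences are also limited. Chance gender imbalance does not bias a randomised comparison, and gender is already a listed covariate. That reply stands in part: under 4.3.2 adjustment for gender is likely but not guaranteed.

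On site, a reader might infer that leaving out a stratification factor invalidates the test. It does not. The error is on the conservative side, and at a 1-point site difference the power loss is about 0.6 percentage points. Section 4.3.1 also leaves room for additional variables from medical record and questionnaire histories, so the factor list is not closed. That does not prespecify site, and the gap is one of prespecification.

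**Conclusion.** The point holds as a gap in specification with a modest cost. Site is the only stratum named, and site strata alone cannot force the gender balance claimed in 2.1.5 and 2.1.2, so the two sections must be reconciled. If gender is not a stratum and half the infants are male, a gap above 10 points has a chance of about 13% overall, 32% at UMass (27–37% depending on how exactly 10 is counted) and 25% at UPitt.

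Site is named in no Aim 1 or Aim 3 model. For Aim 1 this costs power without biasing the estimate or inflating type I error. The loss runs from about 0.6 percentage points at a 1-point site difference to about 4 at 2.5 points, which is a full SD. At an assumed 2 points, power is just under the planned 90%. These losses rest on assumed site differences and on reading the SD of 2.5 as within-site. The site point does not apply to Aim 2, where a site term would have one level.

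**What to change.** **Randomisation (2.1.2 and 2.1.5).** State the strata explicitly as site by infant sex: four strata, with the same random block sizes. Infants enter within 30 hours after birth, so sex can be known at allocation. Otherwise, withdraw the gender-balance claim from both sections. Say whether the UPitt hospitals listed in 2.1.3 count as one site.

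**Analysis (4.3.1, 4.3.2 and 4.3.4).** Prespecify site and sex as fixed effects in every Aim 1 and Aim 3 treatment comparison, outside the R²-based selection. In Aim 2, include sex but no site term.

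**Cost.** A few more incomplete blocks and a few sentences of SAP text. The allocation list needs regenerating only if it was built on site alone.

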	development are also assessed. Administered by Outcomes Specialist. (C)			
Dedictois Evoluction of	(Upload: Bayley Record Form)	Mahilita Osara		
	The PEDI Mobility domain provides a standardized assessment of mobility	Mobility Score		
Disability Inventory ⁽⁰¹⁾ (10 [°])	skills appropriate for children up to the age of 4 years. Administered by			
6mo and 12 mo	Outcomes Specialist or Research Study Staff. (C) (Upload: Pedi Self Care			
	and Mobility)			
Brief Infant Sleep	The BISQ is a modified questionnaire that provides a general assessment of	General Sleep		
Questionnaire (Sadeh, 2004)	infant sleep behaviors. Administered by Outcomes Specialist or Research	Assessments		
1mo, 6mo, 12mo	Study Staff. (P) (Upload modified BISQ)			
	Behavior & Emotional Status of Infant			
Bayley Social and Emotional	The Bayley S&E measures emotional adjustment of infants and toddlers.	Composite Score		
Scale ^[00] (10')	Administered by Outcomes Specialist*. (P) (Upload Bayley Social and			
6mo and 12 mo	Emotional Scale)			
	Parent Intellectual Ability and Psychological Status			
Wechsler Abbreviated Scale	The WASI ii is a short and reliable measure of intelligence in clinical, psycho-	2-Factor IQ		
of Intelligence ^[57]	educational, and research settings and is individually administered. 2			
(20')	subtests will be used to generate a FSIQ: Vocabulary requires individual to			
*1mo	define words of increasing difficulty; Block Design assesses ability to			
	construct two dimensional designs from multicolored blocks. Administered by			
	Outcomes Specialist. (P) (Upload: WASI-II)			
Brief Symptom Inventory-18	The BSI provides a valid assessment of adult psychiatric status, including the	GSI; subtest T-		
1mo (baseline), 6mo, 12mo	domains of depression, anxiety, and somatization. Administered by Outcomes	scores		
	Specialist or Research Study Staff. (P) (Upload BSI)			
Environment and Family Function of Parent				
General Functioning Scale [66]	The McFad is a subscale from McMaster Family Assessment Device	Total score		
(5')	(FAD). 12-item scale is an overall measure of family functioning and has been			
1mo (baseline), 6mo, 12 mo	snown to interact with illness severity and pediatric outcome studies using the			
	changes in family function over time. Administered by Outcomes Specialist or			
	Research Study Staff (P) (Unload: Adapt McEad v1 0)			

Note: 1mo, 6mo, and 12mo time points are approximate testing periods. Assessments will primarily be administered by Outcomes Specialist in the outpatient clinic/office or at home visits, except in some instances:

- 3 1) BSI and McFad questionnaires may be administered in hospital by research study staff to obtain baseline assessment while the infant and/or mom are still in hospital (may be performed by Outcomes Specialist at 1mo outpatient visit if unable to administer while in hospital).
- 2) GOSE-E Peds and BISQ will not be performed at the 1-month time point if the infant is hospitalized at timeframe of testing period; we anticipate all infants will be discharged before the 6mos assessments.
 3) If study staff are unable to do assessments in person (i.e., study staff unable to schedule assessment when subject is in patient, at outpatient aligic/office or home visit) the following

assessment when subject is in-patient, at outpatient clinic/office or home visit) the following questionnaires may be performed by research study staff over the phone: GOS-E-PEDI, PedsQL, PEDI, BISQ, Bayley S&E, BSI, McFad. The Bayley iii measures of neurodevelopment and WASI cannot be performed over the phone.

4) *WASI may be administered anytime throughout the study period by Outcomes Specialist.

